Survival Data Collection			X	Patients that enter the Extension Period will be followed for overall survival assessments up to a maximum of 100 days after the last treatment dose.
Clinical Drug Supplies				
IVRS drug vial assignment	X			
Nivolumab Infusion treatment	X			

^a Follow up Visit 1 and 2 will occur at 40-60 days and 101-120 days after the stop of study therapy, respectively. Efficacy is required at Follow up visit 2 only.

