Procedure	Treatment Cycle = IV infusion q 2 weeks for 8 weeks				End of Treatment Visit	Notes
	Day 1	Day 15	Day 29	Day 43		
Safety Assessments						
Physical Examination	X	X	X	X	X	Done weekly in Cycle 1; to include body weight
Vital Signs (including ECOG Performance status)	X	X	X	X	X	Measured before and after study drug administration. Includes body temperature, respiratory rate, seated blood pressure and heart rate. Blood pressure and heart rate should be measured after the subject has been seated quietly for at least 5 minutes. Done weekly in Cycle 1 only.
Pulse oximetry	X	X	X	X	X	Collected at rest for at least 5 minutes, before each study drug administration. Oxygen levels will be used in combination with clinical signs and symptoms and radiographic images to evaluate pulmonary/respiratory status. Changes in O ₂ levels will not be used in isolation to document or diagnosis pulmonary toxicity.
Monitor for Adverse Events	X	X	X	X	X	All Non-Serious Adverse Events will be collected from Day1 until the subject's 100 days post discontinuation of dosing or subject's participation in the study if the last scheduled visit occurs at a later time All Serious Adverse Events must be collected from the date of the subject's written consent until 100 days post discontinuation of dosing or subject's participation in the study if the last scheduled visit occurs at a later time
Review Concomitant medications	X	X	X	X	X	
Laboratory Tests	X	X	X	X	X	To include CBC with differential, Complete Metabolic Panel (Na, K, Cl, CO ₂ , BUN, Cr, eGFR, AST, ALT, Alk Phos, Albumin, Total Bilirubin, Total Protein, Calcium, glucose), direct bilirubin, lipase, LDH, magnesium, phosphorus

Table 5.1B: CA209038 Treatment Procedural Outline, Part 1 (Cohorts 1 and 2)						
Procedure	Treatment Cycle = IV infusion q 2 weeks for 8 weeks				End of Treatment Visit	Notes
	Day 1	Day 15	Day 29	Day 43		
ECG	X				X	Single 12-lead ECGs will be collected at screening and prior to dosing on Day 1 of every other treatment cycle starting with Cycle 1. On Day 1 of Cycles 1, 2, and 4, an End of Infusion (EOI) ECG will be collected, as well. Electrocardiogram recording should be obtained just prior to as the serial PK samples as indicated in Table 5.5A.
Chest radiograph						As clinically indicated
Serum or Urine Pregnancy Test	X		X		X	Starting with Day 1 and then every other dose or every 28 days. For WOCBP within 24 hours of Study Drug Administration
Serum TSH	X					On Day 1 of each cycle
Exploratory						

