Blood samples for PK, ADA, Biomarkers	See Table 5.5A for timing of samples					
Efficacy Response Assessments						
Disease assessment, Tumor Imaging (CT or MRI of Chest/Abdomen/Pelvis; MRI brain if clinically indicated)				X (between days 49-56)	X	Tumor assessments should be done every 8 wks (+/- 1 wk) until confirmed disease progression is documented or follow-up is completed. Methods used at baseline should be continued throughout study. MRI of brain are only required if clinically indicated
Clinical Drug						
Dispense Study Drug/Treatment	X	X	X	X		Nivolumab will be administered as an IV infusion on Days 1, 15, 29, 43 of each 56 day treatment cycle (8 weeks/cycle)

Table 5.1C: CA209038 Follow-up Visits - Part 1 (Cohorts 1 and 2)		
Procedure	Follow-up Visit 1 (40-60 days) and Visit 2 (101-120 days)	Notes
Safety Assessments		
Physical Examination	X	
Vital Signs (including ECOG)	X	Includes body temperature, respiratory rate, pulse oximetry, seated blood pressure and heart rate. Blood pressure, pulse oximetry and heart rate should be measured after the subject has been seated quietly for at least 5 minutes
Adverse Events Assessment	X	For study related adverse events only
Review Concomitant Medications	X	
Laboratory Tests	X	To include CBC with differential, Complete Metabolic Panel (Na, K, Cl, CO ₂ , BUN, Cr, eGFR, AST, ALT, Alk Phos, Albumin, Total Bilirubin, Total Protein, Calcium, glucose), direct bilirubin, lipase, LDH, magnesium, phosphorus, TSH
Serum or Urine Pregnancy Test	X	
ECG	X	12 Lead; for the first two follow-up visits only. Measurement should be recorded after the subject has been supine for at least 5 minutes
Tumor biopsy	X (encouraged, not mandated)	Upon confirmed progression May be done at either Follow-up visit 1 or Follow-up visit 2

Table 5.1C: CA209038 Follow-up Visits - Part 1 (Cohorts 1 and 2)		
Procedure	Follow-up Visit 1 (40-60 days) and Visit 2 (101-120 days)	Notes
Efficacy Assessments		
Disease assessment (CT/MRI)	X	Done after 12 weeks from the last on-study scan during Follow-up Visit 1 OR 2 then Q12wks by methods used at baseline Not required for subjects entering follow-up period for confirmed disease progression
Exploratory		
Blood samples for PK, ADA	X	As per Table 5.5A

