Survival Status	X	Survival status should be continued every 3 months for the time remaining after the last office follow-up visit until 2 years from the first dose of BMS-936558 or until subject death, subject withdraws consent, subject is lost-to follow-up or the study is completed. This may be accomplished by visit or phone contact.

Table 5.1D: On Treatment Procedural Outline (CA209038) - Part 2, Part 3 and Part 4: Arms A and D								
[Procedure Window ± 2 days]								
Procedure	Wk1 Day 1	Wk4 Day 1	Wk7 Day 1	Wk10 Day 1	Wk 13 Day 1 and every 2 weeks thereafter	End of Therapy	Follow- Up Visits 1 and 2^a	Notes
Safety Assessments								
Targeted Physical Examination	X	X	X	X	X	X	X	To be performed only as clinically indicated
Vital Signs and Oxygen Saturation	X	X	X	X	X	X	X	Including BP, HR, temperature and oxygen saturation by pulse oximetry. Pulse oximetry at rest and after exertion within 72 hours prior to dosing
Physical Measurements (including performance status)	X	X	X	X	X	X	X	Weight and ECOG performance status
Adverse Events Assessment	X	X	X	X	X	X	X	Continuously throughout the study
Review of Concomitant Medications	X	X	X	X	X	X	X	
12 Lead ECG					X*			*To be performed pre-dose at Week 13, Week 23 and then every 16 weeks thereafter

Table 5.1D: On Treatment Procedural Outline (CA209038) - Part 2, Part 3 and Part 4: Arms A and D									
[Procedure Window ± 2 days]									
Procedure	Wk1 Day 1	Wk4 Day 1	Wk7 Day 1	Wk10 Day 1	Wk 13 Day 1 and every 2 weeks thereafter	End of Therapy	Follow- Up Visits 1 and 2 ^a	Notes	
Laboratory Tests									
Serum Chemistry	X	X	X	X	X		X	X	Within 72 hours prior to re-dosing to include: Aspartate aminotransferase (AST), Alanine aminotransferase (ALT), total bilirubin, alkaline phosphatase, lactate dehydrogenase, creatinine, blood urea nitrogen (BUN) or serum urea level, amylase, lipase, glucose, sodium, potassium, chloride, CO ₂ calcium, magnesium, TSH (if TSH is abnormal then obtain free T3 and free T4), ACTH collected in the morning as clinically indicated.
Hematology	X	X	X	X	X		X	X	Within 72 hours prior to re-dosing to include CBC with differential NOTE: Additionally required for the PBMC sample collection at the following timepoints: Week 1 Day 4; Week 2 Day 1; Week 3 Day 1; and Week 5 Day 1
Pregnancy Test (WOCBP only)	X	X	X	X	X	X	X	X	Serum or urine within 24 hours prior to administration of study drug

Table 5.1D: On Treatment Procedural Outline (CA209038) - Part 2, Part 3 and Part 4: Arms A and D								

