5.3 Safety Assessments

At baseline, a medical history will be obtained to capture relevant underlying conditions. Baseline signs and symptoms are those that are assessed within 2 weeks prior to treatment arm assignment. The baseline physical examination should include: weight, height, ECOG performance status, blood pressure, heart rate, electrocardiogram, O₂ saturation (pulse oximetry) and temperature; it should be performed within 28 days of treatment arm assignment. Concomitant medications will be collected from within 2 weeks prior to treatment arm assignment through the study treatment period (see [Table 5.1A](#), [Table 5.1B](#), [Table 5.1C](#), [Table 5.1D](#), and [Table 5.1E](#)).

Subjects will be considered evaluable for safety if they have received any study drug.

Toxicity assessments will be continuous during the treatment phase and follow-up phases.

Performance status and body weight should be assessed at each on study visit. Vital signs should also be taken as per institutional standard of care prior to, during and after the infusions with investigational products. Pulse oximetry should be done prior to each infusion as well. The start and stop time of the study drug infusion should be documented. If there are any new or worsening clinically significant changes since the last exam, report changes on the appropriate non-serious or serious adverse event page.

Additional measures including non-study required laboratory tests should be performed as clinically indicated.

Safety assessments will be based on the medical review of adverse event reports, results of vital sign measurements, Eastern Cooperative Oncology Group (ECOG) performance status, physical examinations, clinical laboratory results, ECGs, and imaging tests.

The incidence of observed adverse events will be categorized using the most current version of MedDRA and reviewed for potential significance and clinical importance. Adverse events will

be evaluated according to the National Cancer Institute Common Terminology Criteria for Adverse Events (NCI CTCAE) version 4.0.

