6.1.1 Serious Adverse Event Collection and Reporting

Following the subject's written consent to participate in the study, all SAEs, whether related or not related to study drug, must be collected, including those thought to be associated with protocol-specified procedures. All SAEs, of any causality, must be collected that occur during the screening period and within 100 days of discontinuation of dosing for those subjects that receive study therapy (within 30 days of last visit for enrollment failures). If applicable, SAEs must be collected that relate to any later protocol-specified procedure (e.g., a follow-up skin biopsy).

The investigator should report any SAE occurring after these time periods that is believed to be related to study drug or protocol-specified procedure.

An SAE report should be completed for any event where doubt exists regarding its status of seriousness.

If the investigator believes that an SAE is not related to study drug, but is potentially related to the conditions of the study (such as withdrawal of previous therapy, or a complication of a study procedure), the relationship should be specified in the narrative section of the SAE Report Form.

SAEs, whether related or not related to study drug, and pregnancies must be reported to BMS (or designee) within 24 hours. SAEs must be recorded on the SAE Report Form; pregnancies on a Pregnancy Surveillance Form (electronic or paper forms). When using paper forms, the reports are to be transmitted via email or confirmed facsimile (fax) transmission to:

SAE Email Address: See Contact Information list.

SAE Facsimile Number: See Contact Information list.

For studies capturing SAEs/pregnancies through electronic data capture (EDC), electronic submission is the required method for reporting. The paper forms should be used and submitted immediately, only in the event the electronic system is unavailable for transmission. When paper forms are used, the original paper forms are to remain on site.

SAE Telephone Contact (required for SAE and pregnancy reporting): See Contact Information list.

If only limited information is initially available, follow-up reports are required. (Note: Follow-up SAE reports should include the same investigator term(s) initially reported.)

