8.3.2 Secondary Endpoint(s)

8.3.2.1 Safety

The secondary objective relates to safety and tolerability of nivolumab and nivolumab in combination of ipilimumab in subjects with advanced melanoma. These will be measured by the following endpoints:

Incidence rate of adverse events, serious adverse events, and deaths: all non-serious adverse events will be collected from Day 1 until 100 days after the subjects last dose of therapy or until they discontinue the study as per [Section 3.1](#). All serious adverse events must be collected from the date of the subjects' written consent until 100 days after discontinuation of dosing or until they discontinue the study as per [Section 3.1](#).

Occurrence of clinical laboratory test abnormalities including hematology and serum chemistry abnormalities assessed at specified timepoints as designated in the Time and Events Section ([Section 5.1](#)). Safety labs are listed in [Section 5.3.1](#).

Vital signs: Changes in vital signs relative to baseline including blood pressure and heart rate measurements. These will be measured at time points designated in the Time and Events Section ([Section 5.1](#)).

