4.2 Secondary Endpoints

4.2.1 Safety and Tolerability

The secondary objective relates to safety and tolerability of nivolumab and nivolumab in combination of ipilimumab in subjects with advanced melanoma. These will be measured by the following endpoints:

- Incidence rate of adverse events (AEs), serious adverse events (SAEs), select AEs, AEs leading to discontinuation, and deaths.
 - All non-serious AEs will be assessed from the start of dosing.
 - All SAEs and deaths will be assessed from the date of the subject's written informed consent.
 - All AEs (serious and non-serious), and deaths will be assessed up to 100 days after the subject's last dose of study drug or until they discontinue the study as per Protocol Section 3.1².
 - Select AE categories are captured in Table 11-3 of the core safety SAP for CA209³. This list is subject to change and may not necessarily reflect the categorizations at each database lock. A separate listing will be provided for the categorizations at each analysis.
 - Immune modulating AEs may also be summarized
- Occurrence of clinical laboratory test abnormalities including hematology and serum chemistry abnormalities will be examined.
- Vital signs: Changes in vital signs relative to baseline including blood pressure and heart rate measurements.
- Other safety endpoints include changes in or incidence of: weight, height, Eastern Cooperative Oncology Group (ECOG) performance status, electrocardiogram abnormalities, and O₂ saturation (pulse oximetry).

Adverse events will be categorized using the most current version of the Medical Dictionary for Regulatory Activities (MedDRA) at the time of each database lock; both AEs and laboratory values will be graded according to the National Cancer Institute (NCI) Common Terminology Criteria for Adverse Events (CTCAE) version 4.0.

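### The Part 1 follow-up schedule limits adverse event assessment to study-related events, contradicting the all-cause 100-day rule for the same subjects and risking incomplete non-serious AE data

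*Protocol*

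**What the plan says.** **The restrictive instruction.** Protocol Table 5.1C applies only to Part 1. In its adverse event row, for Follow-up Visit 1 (days 40-60) and Follow-up Visit 2 (days 101-120), the note reads "For study related adverse events only".

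**The all-cause instructions that also apply to Part 1.**
- Table 5.1B, the treatment schedule for the same cohorts: "All Non-Serious Adverse Events will be collected from Day1 until the subject's 100 days post discontinuation of dosing", extended to a later last scheduled visit where there is one.
- Protocol Section 8.3.2.1: "all non-serious adverse events will be collected from Day 1 until 100 days after the subjects last dose of therapy", or until the subject leaves the study.
- Protocol Section 5.3: "Toxicity assessments will be continuous during the treatment phase and follow-up phases".
- Protocol Section 6.1.1, for serious events: "all SAEs, whether related or not related to study drug, must be collected".
- SAP Section 4.2.1: "All AEs (serious and non-serious), and deaths will be assessed up to 100 days after" the last dose, with the same alternative end at study discontinuation. SAP Section 7.6 uses the 100-day window for its AE summaries.

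**Parts 2 to 4.** Tables 5.1D, 5.1E and 5.1F describe adverse event assessment as "Continuously throughout the study", with both follow-up visits marked and no reference to relationship.

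**The concern.** Protocol Section 3.6 sends sites to Section 3.1 and the Section 5.1 tables for post-treatment follow-up. For a Part 1 subject who has stopped dosing, the table listing the visit procedures is 5.1C. Table 5.1B's columns end at the End of Treatment visit, and Section 8.3.2.1 sits in the statistics chapter. A coordinator preparing Follow-up Visit 1 could reasonably act on the narrow instruction, although that visit lies well inside the all-cause window.

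Three analyses would then be affected.
- SAP Sections 7.6.5 and 7.6.6 tabulate adverse events of any relationship separately from drug-related ones, by part, by cohort or arm, and overall. The overall columns would mix two collection rules.
- SAP Section 7.6.7 divides events by person-time that includes the 100 days after the last dose. Unrecorded events reduce the numerator and leave the denominator unchanged.
- SAP Section 7.6 counts an event with missing relationship as drug-related. That safeguard cannot act on an event that was never entered. Because relationship is an investigator judgement in an open-label study, an omitted event also cannot be reassessed later.

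**Working it through.** **1. Who is covered by the note.** Planned sizes from Protocol Section 3.1: Part 1 has two cohorts of about 40, Part 2 about 20, Part 3 about 30, Part 4 about 20.

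2 × 40 + 20 + 30 + 20 = 150, which reproduces the stated total. Part 1 share = 80 / 150 = 53%.

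**2. Which events are exposed.**

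| Type of event in Part 1 | Instruction that captures it | Exposed to the note? |
|---|---|---|
| Any event up to the End of Treatment visit | Table 5.1B | No |
| Serious event, any causality, to 100 days | Section 6.1.1, Table 5.1B | No |
| Clinically significant laboratory result | Section 6.3 | No |
| Significant worsening on examination or ECG | Section 6.7; both are scheduled in Table 5.1C | No |
| Non-serious, drug-related | Table 5.1C itself | No |
| Late-emerging non-laboratory drug-related toxicity after 100 days | Section 6.2.1 | No |
| Other non-serious, judged unrelated, End of Treatment visit to day 100 | Table 5.1B, Section 8.3.2.1 and the SAP say collect; Table 5.1C says do not | **Yes** |

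Follow-up Visit 2 falls after day 100, so within the 100-day window it matters only for the look-back it provides. Follow-up Visit 1 falls wholly inside the window. The term used in the note is not defined: Section 6 defines relationship to study drug only, so a site could also wonder whether procedure-related events count.

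**3. How much person-time is involved.** For a subject off treatment and followed for at least 100 days, SAP Section 7.6.7 gives person-time of T + 101 days, where T is the number of days from first to last dose. The documents give no expected T, so the values below are assumptions. The first share is 100 / (T + 101). The second counts days 15 to 100 (86 days), because SAP Section 6.1.3 starts follow-up 15 days after the last nivolumab dose. That is an analysis definition, not a collection rule.

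| T | T + 101 (days) | 100 days after last dose | Days 15-100 |
|---|---|---|---|
| 16 weeks (112 days) | 213 | 47% | 40% |
| 24 weeks (168 days) | 269 | 37% | 32% |
| 52 weeks (364 days) | 465 | 22% | 18% |
| 104 weeks (728 days) | 829 | 12% | 10% |

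**4. Illustration of the effect on a rate.** Assume a constant event rate over this person-time, and that a fraction f of events in days 15-100 goes unrecorded. The relative loss in the all-cause rate is f × 86 / (T + 101).

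| T | f = 0.25 | f = 0.50 | f = 0.75 |
|---|---|---|---|
| 16 weeks | 10% | 20% | 30% |
| 24 weeks | 8% | 16% | 24% |
| 52 weeks | 5% | 9% | 14% |
| 104 weeks | 3% | 5% | 8% |

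Both f and the constant rate are assumptions; nothing in the documents supports a particular cell. The calculation also takes the Section 7.6.7 numerator to cover the Section 7.6 window. That section speaks of on-treatment events, and if it were read as the SAP Section 6.1.2 treatment period, follow-up events would not enter the numerator at all.

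**The case against.** The strongest reply is that full collection is already required. Table 5.1B states the all-cause rule for the same cohorts and the same 100 days, Section 8.3.2.1 repeats it, and Section 5.3 makes assessment continuous through follow-up. A site reading the whole protocol would collect everything. This stands to the following extent: a reader might infer that the all-cause endpoint is in fact under-collected in 80 subjects, and the documents do not show that. They show two incompatible instructions and do not say which one sites followed.

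It can also be said that incidence tables are insensitive to the gap. SAP Section 7.6 counts a subject once per preferred term, once per system organ class and once in total, at worst grade. A missed late event changes nothing if the subject already has that term at the same or a worse grade. This is correct, and it means that missing events do not translate one for one into lower incidence. It does not protect the Section 7.6.7 rates, which count repeated occurrences.

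A reader might also infer that the note undermines the combination of Cohort 1 with Arm B. It does not. Protocol Section 8.4.2 specifies that combination for efficacy and Section 8.4.4 allows it for pharmacokinetics; protocol safety tables are by cohort or arm. The comparability concern rests instead on the SAP's overall safety columns, on side-by-side reading of the parts, and on the optional pooling in SAP Section 7.1, which is conditional on comparable data.

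**Conclusion.** The Table 5.1C note contradicts Table 5.1B, Protocol Section 8.3.2.1 and SAP Sections 4.2.1 and 7.6, and the passages must be reconciled. It applies to about 80 of 150 planned subjects (53%), and only to Part 1. The events at risk are mainly non-serious ones judged unrelated that arise between the End of Treatment visit and day 100.

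If sites followed the note, all-cause AE summaries for Cohorts 1 and 2 and the exposure-adjusted rates could be too low and would rest on a different collection basis from Parts 2 to 4. The size of any shortfall cannot be determined: the documents give neither treatment duration nor the share of late events judged unrelated. For the same reason, no number of affected subjects beyond the 80 covered by the note can be supported. Safety is a secondary objective and the correction is small, so it should be made.

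**What to change.** Replace the Table 5.1C note with the Table 5.1B collection rule: all serious and non-serious adverse events, whatever their relationship, until 100 days after dosing stops or until the last scheduled visit if that is later. After that point, late-emerging drug-related toxicity continues to be reported under Section 6.2.1. Restricting collection to drug-related events from day 100 onward would not do, because Follow-up Visit 2 is at days 101-120 and Table 5.1B extends all-event collection to a later last visit. Send Part 1 sites a reminder with the change.

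Protocol Section 4.3 places Part 1 enrolment before Amendment 04, and Section 8.4 already refers to Amendment 06, so some Part 1 subjects may have finished follow-up. For them, query sites for unrecorded events where source records allow, and state in the clinical study report that post-treatment, non-serious, unrelated adverse events may be incomplete in Cohorts 1 and 2.

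The cost is one table line, a site reminder, slightly more AE entry at visits already scheduled, and the query effort for completed subjects.
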